### **Associated Areas of Functioning**

- Deployment Risk and Resiliency Inventory-2 (DRRI-2): The DRRI-2 (Vogt et al., 2012) is a suite of 17 individual scales that assess key deployment-related risk and resilience factors with demonstrated implications for Veterans' long-term health. The following subscales will be used to assess deployment factors: Combat Experiences. We will use the Post-Deployment Life Events and Support scales to evaluate post-deployment factors for Veterans.
- CNS Vital Signs Cognitive Testing: A battery of two tests (Stroop & Shifting Attention) will assess neurocognitive functions.

**Compensation:** Participants will be compensated \$50 for the baseline visit, \$50 for each imaging visit, \$40 for each completed weekly visit, and \$75 for completing each of the follow-up visits. They will be given a \$25 bonus if the baseline/first visit is attended as scheduled. Participants who previously consented to the optional neuropeptide Y will receive \$15 compensation for completing the second blood draw. Thus, participants may receive up to \$755 for completing all visits. Compensation is available in the form of cash, gift card, or check.

Telehealth participants will be offered compensation for travel to and from the three mandatory in-person visits (Baseline, Week 4, & Week 8).

**Neuroimaging Component:** Given the severe negative outcomes associated with co-occurring AUD/SUD and PTSD and lack of effective treatments, investigation of the neural circuitry and neurochemistry underlying AUD/SUD/PTSD and involved in positive therapeutic response could be important in guiding future treatment development studies. To that end, fMRI and H-MRS data will be acquired at baseline and end of treatment on a subset (n=40) of participants to examine (a) glutamate concentrations, (b) resting state connectivity, and (c) response to alcohol/drug, trauma, and neutral cues. Scans will be conducted at the MUSC Center for Biomedical Imaging.

The neuroimaging component will involve three visits, each lasting 60-90 minutes. During visit 1, we will develop the personalized imagery scripts for alcohol/drug, trauma, and neutral cues. During visit 2 (pre-treatment) and visit 3 (end of treatment), we will conduct the fMRI and H-MRS scanning procedures. Imagery scripts will be similar to those developed according to standardized procedures (Sinha & Li, 2007) and employed in our ongoing research.

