## Protocol: Glial Regulators for Testing Comorbid Posttraumatic Stress Disorder and Substance Use Disorders

Following auto-shimming, single-voxel water-suppressed  $^1\text{H}$ -MRS spectra will be acquired using a Point Resolved Spectroscopy (PRESS) sequence: Repetition Time (RT) = 2000ms; Echo Time (TE) = 40ms; number of averages = 128; an unsuppressed water spectrum will be co-acquired (TE = 40ms, number of averages = 16), scaled for partial volume effects and relaxation, and used as a concentration reference (Mullins et al., 2008).

Participants will be asked to relax and keep their eyes opened and fixed on a cross-hair for two six-minute runs while resting state data are collected. Following this, participants will be exposed to alcohol/drug, trauma and neutral cues, which will be audio recorded descriptions of the most recent time they used alcohol/drug, details of a traumatic event, and details about a relaxing event.

We will use a block design consisting of a single run in which 4 task blocks alternate with rest blocks. The 4 task blocks consist of a neutral cue followed by a trauma cue followed by a neutral cue then an alcohol/drug cue. To minimize potential carry-over effects, the order of task blocks will be counterbalanced so that half of the subjects in the placebo group and half of the subjects in the NAC group are exposed to the alcohol/drug cue first and the remaining participants in each group are exposed to the trauma cue first. This order will be repeated at the end of treatment scan. T2\*-weighted gradient-echo planar images (EPI) will be acquired with the following parameters: TR = 1100ms, TE = 30ms, flip angle =  $65^\circ$ , matrix 64 x 64, field of view = 192mm, slice thickness = 3.0mm, with 48 slices to cover the entire brain.

**Statistical Analyses:** Baseline clinical and demographic characteristics will be collected and contrasts performed between treatment groups. Baseline characteristics found to be significantly associated with primary outcome measures will be included as covariates in the analyses. In general, less than 10% missing data have little impact on power and do not introduce bias, regardless of the missing data mechanism. If the percent missing data are greater than 10%, propensity score methods will be used for data imputation.

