For hypotheses 3A and 3B, the following preprocessing and analytical parameters will be used. Preprocessing: Post-acquisition preprocessing and statistical analysis of imaging data will be performed using FEAT (FMRI Expert Analysis Tool) Version 5.98, part of FSL (FMRIB's Software Library). Data will be preprocessed using scripting tools from FEAT. Non-brain signal will be removed using FSL's BET brain extraction. Scans will be corrected for motion using FSL's linear registration and scans will be spatially smoothed. Participants with head motion  $\geq 0.2$  mm will be excluded from the analyses (Power et al., 2012). Motion artifacts will be identified and scrubbed from each subject's data. Scans will be spatially co-registered with a standardized anatomical template (Montreal Neurological Institute) using a 12 parameter affine transformation. Analysis: Functional connectivity will be measured using a psychophysiological interaction (PPI) seed-based approach (Friston et al., 1997). PPI analysis is used to assess the functional coupling between different brain regions. The PPI is defined as the change in connectivity of one area (i.e., the seed region) to another in relation to the experimental context (e.g., alcohol vs. neutral cues). PPI analyses for resting state, trauma and alcohol/drug cues will be performed separately. Customized sq. wave forms representing the trauma run (1=trauma block and -1=neutral block) and the alcohol/drug cue run (1=alcohol/drug block and -1=neutral block) will be convolved with a double-gamma hemodynamic response function. A mask of the seed region will be made using a 12-mm diameter sphere located in the center of the AMY using the MNI coordinates (x, y, z =  $\pm 22, 0, -22$ ). The transformation parameters described above will also be applied to the mask. For each subject, the mean corrected and high pass filtered time series of the BOLD signal in the AMY will be extracted and used in a single subject whole brain PPI analysis. The PPI model will include the task vector, time series of the BOLD signal in the AMY, a term representing the positive task x seed interaction, and a term representing the negative task x seed interaction. The first level analysis will generate contrast images of the parameter estimates for each of the four regressors. Voxels will be thresholded at  $Z > 2.3$  using a corrected cluster threshold of  $p=0.05$ . The contrast images of the parameter estimates of the positive and negative task x seed interactions will be combined for group-level t-tests to identify regions that exhibited altered connectivity with the AMY during the trauma and alcohol/drug cues as compared to neutral cues. All group-level results will be thresholded at  $Z > 2.3$  using a corrected cluster threshold of  $p=0.05$ . Separate linear regression tests will be used to test for associations between PFC-AMY connectivity at baseline and improvement in AUD/SUD and PTSD symptoms during treatment. Changes in total standard drinks will be

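### The 5% cluster-corrected error rate for the Hypothesis 3 group maps is not assured at Z > 2.3 if FEAT's parametric correction is used; permutation inference on the same images would bring it close to 5%

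*Combined protocol and SAP*

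**What the plan says.** The analysis paragraph for Hypotheses 3A and 3B (Statistical Analyses, Hypotheses) says that imaging analysis will be "performed using FEAT (FMRI Expert Analysis Tool) Version 5.98, part of FSL (FMRIB's Software Library". Of smoothing it says only that "scans will be spatially smoothed", with no kernel. The amygdala time series is "used in a single subject whole brain PPI analysis", so the search covers the whole brain. First-level contrast images are then "combined for group-level t-tests to identify regions that exhibited altered connectivity with the AMY during the trauma and alcohol/drug cues". For these maps, "All group-level results will be thresholded at" Z > 2.3 "using a corrected cluster threshold of" p=0.05.

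The paragraph does not name the correction method (parametric or permutation) or the sidedness of the t-tests, and it plans no check of the error rate. It goes on to regress change in total standard drinks (3A) and change in CAPS-5 (3B) on the estimate at the central voxel of every significant cluster. The threshold therefore decides which predictors exist and how many.

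The Neuroimaging Component gives the functional acquisition as "matrix 64 x 64, field of view = 192mm, slice thickness = 3.0mm, with 48 slices to cover the entire brain", and states that imaging data "will be acquired at baseline and end of treatment on a subset (n=40) of participants".

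**The concern.** A parametric random-field cluster test summarises the noise by a single smoothness, estimated from neighbouring voxels, and assumes that spatial correlation falls off as a Gaussian curve. At a low cluster-forming level such as Z > 2.3 (one-sided voxel p = 0.0107) clusters are large, so their size under the null depends on correlation over longer distances, which that summary does not capture. If the real correlation has a longer tail, the nominal 5% understates the chance of a false cluster; if it is Gaussian, the test can be stricter than stated.

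Two things are at stake. The surviving clusters are to be reported as findings about connectivity, and they are the gateway to the Hypothesis 3 regressions. Too lenient a rule lets noise regions in; too strict a rule keeps real ones out.

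**Working it through.** **Inputs from the documents.** Cluster-forming Z > 2.3; corrected p = 0.05; whole-brain search; voxels 192/64 = 3 mm in plane, 3 mm slices, 48 slices; n = 40 before motion exclusions.

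**Assumptions (not in the documents).** FEAT's parametric random-field correction; group maps on the 3 mm acquisition grid (the plan registers scans to a standard template and gives no group-map resolution); an ellipsoid mask of V = 57,232 voxels (1.55 L); stationary noise; one-sample tests. Noise correlation at distance r (mm) is either Gaussian, or the mixture a·exp(−r²/2b²) + (1−a)·exp(−r/c).

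**Step 1: the extent cut-off that nominal 5% implies.** With F the smoothness in voxels, u = 2.3 and Q(u) = 0.0107:

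- |Λ|^½ = (4 ln 2)^1.5 / F³. For 6 mm, F = 2, giving 4.617/8 = 0.577.
- Expected clusters: Em = V(2π)⁻²|Λ|^½(u²−1)exp(−u²/2) = 57,232 × 0.02533 × 0.577 × 4.29 × 0.0710 = 254.8.
- β = (Γ(2.5)·Em / (V·Q))^(2/3) = (1.329 × 254.8 / 613.8)^(2/3) = 0.673.
- Setting 1 − exp(−Em·exp(−βk^(2/3))) = 0.05 gives k = (ln(254.8/0.0513)/0.673)^1.5 = 45 voxels. For 8 mm the same steps give 91.

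**Step 2: why smoothness does not settle it.** Compare Gaussian noise of 6 mm FWHM with the mixture a=.7, b=3.5, c=10.

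- At one voxel (3 mm): Gaussian 2^(−2·9/36) = 0.707; mixture .7·exp(−9/24.5) + .3·exp(−.3) = 0.707. The estimated smoothness and the cut-off of 45 voxels are the same.
- At 12 mm: Gaussian 2^(−2·144/36) = 0.004; mixture .7·exp(−144/24.5) + .3·exp(−1.2) = 0.092.

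**Step 3: actual error rate at nominal 5%.** Simulated null Z maps, 800 per row, clusters joined over 26 neighbours; the one-direction rate averages the two tails.

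| Noise | Estimated FWHM (mm) | Cut-off (voxels) | One direction | Both directions read |
|---|---|---|---|---|
| Gaussian | 5 | 29 | 2.4% | 4.8% |
| Gaussian | 6 | 45 | 3.1% | 5.8% |
| Gaussian | 8 | 91 | 1.9% | 3.6% |
| Gaussian | 10 | 155 | 1.9% | 3.7% |
| Gaussian | 12 | 236 | 2.5% | 4.9% |
| Mixed a=.9, b=5, c=12 | 8.2 | 96 | 7.6% | 14.6% |
| Mixed a=.8, b=5, c=12 | 8.0 | 92 | 15.4% | 28.5% |
| Mixed a=.7, b=3.5, c=10 | 6.0 | 45 | 34.2% | 59.1% |
| Mixed a=.6, b=5, c=15 | 8.2 | 95 | 37.9% | 63.7% |

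A separate run of 400 maps gave 6.3% for the lightest tail. Heavier tails go higher (60.7% for a=.5, b=3.5, c=12; 86.3% for a pure exponential with c=10), but the conclusion does not rest on them. Monte Carlo 95% half-widths are about 0.7 points near 2% and 2.3 points near 34%.

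**Step 4: the same with n = 40.** One-sample t maps, smoothness estimated from residuals, 150 runs each: 3.3% and 0.7% for Gaussian noise of 6 and 8 mm; 32.7% (a=.7) and 36.0% (a=.6) for mixed noise, each of these two with a half-width of about 7.5 points.

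**Step 5: permutation at the same Z > 2.3.** Sign-flipping the maximum cluster extent in the Step 4 settings gave 5 of 150 (Gaussian 8 mm), 10 (Gaussian 6 mm), 9 (a=.7) and 12 (a=.6). Pooled: 36/600 = 6.0%, 95% CI 6.0 ± 1.9, or 4.1-7.9%, compatible with 5%.

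**Step 6: raising the threshold alone.** Parametric correction at Z > 3.1 gave 1.8-3.1% for Gaussian noise and 4.0-16.9% across all the mixtures, including a=.5. That reduces the dependence on noise shape but does not remove it.

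**The case against.** The strongest reply is that all of this is conditional. The plan does not name the correction method; if permutation was intended, the 5% holds approximately. Nor does it give the kernel or the noise correlation, and some light-tailed shape would land on 5% by chance. Reading both directions under Gaussian noise also gives about 5%. This stands: a reader might infer from the upper rows that the trial's maps will be wrong a third of the time, but the documents support no statement about the actual rate or its direction.

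Second, a reader might take the whole-brain figures as the risk to Hypothesis 3. They are not. Hypothesis 3 concerns prefrontal-amygdala connectivity, so on a natural reading only prefrontal clusters become predictors. Counting only clusters centred in the front 15-25% of the mask (an assumed prefrontal share; 400 maps per case) gave 1-2% for the lightest tail, 2-3% for a=.8, 5-9% for a=.7, 8-13% for a=.6, and 1% or less for Gaussian noise. The figure relevant to the predictors is thus clearly lower.

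Third, a reader might infer that the Hypothesis 3 p-values are inflated. Clusters are chosen on the group mean, not on the outcome, so a noise predictor is still tested at its own nominal level. The data-dependent number of regressions is a separate matter that this change does not resolve.

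Fourth, permutation is not assumption-free: sign-flipping needs symmetric errors, and between-group comparisons need exchangeable labels. That also stands, and it shapes the fix.

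What survives is that the stated 5% depends on a noise shape that the plan neither specifies nor checks, and that estimated smoothness cannot reveal.

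**Conclusion.** The point holds as a limited one. If FEAT's parametric random-field correction is meant, the stated 5% family-wise rate is not assured: about 2-3% with Gaussian-shaped noise and about 6-40% with light to moderate longer tails (whole brain, one direction), at similar estimated smoothness. These figures rest on the assumed method, 3 mm group grid, ellipsoid mask, stationary noise and tail shapes. The consequence is confined to the imaging subset and Hypothesis 3: unreliable connectivity maps, and noise regions entering, or real ones missing from, the regressions. Hypotheses 1 and 2 are untouched. It is worth changing because the remedy is cheap and worked under both noise types.

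**What to change.** Replace the parametric cluster correction for group maps with permutation inference at family-wise p<.05 on the same first-level contrast images. Use sign-flipping for one-sample tests, noting the assumption of symmetric errors, and permutation of treatment labels for the between-medication-group comparisons. State the smoothing kernel and whether each contrast is read in one direction or both, with the 5% applied accordingly. If permutation was already intended, say so.

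Z > 2.3 can be kept as the cluster-forming level; a higher level or threshold-free enhancement is optional.

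The cost is a revised sentence or two and some computing time, with no change to data collection. The downside is that some weak, extended clusters may no longer pass.

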## Protocol: Glial Regulators for Testing Comorbid Posttraumatic Stress Disorder and Substance Use Disorders

total number of standard drinks consumed and the OCDS total score as the primary outcomes. A Poisson distribution will be assumed with a logarithm link function to assess the effects of NAC treatment. Data collected in substance abuse studies often contain a preponderance of zeros, and these zeros in the distribution can be considered sampling zeros in the Poisson process (Bandyopadhyay et al., 2011). If this excess is present in the distribution, two-part Hurdle models (Poisson and NB) will be explored (Cragg et al., 1971). The hurdle part of the model will allow us to estimate the probability of abstinence during the study period (as an odds ratio) while the Poisson/NB portion will allow for the assessment of the risk of an increase in using days beyond zero during the study period (as a risk ratio). Baseline alcohol/substance use and craving will be included in pertinent models as covariates. Additional alcohol/substance use outcomes will be assessed: change in percent drinking days, percent heavy drinking days, EtG, and VAS craving levels.

Hypothesis 2: NAC treatment will result in significantly greater reduction in PTSD severity (CAPS-5) as compared to placebo. To test this hypothesis, generalized linear mixed effects regression models with a Gaussian distribution will be developed to assess group differences while adjusting for baseline CAPS-5 scores. Assumptions of residual normality and homoscedasticity will be checked using statistical test and graphical methods (Residual and Q-Q plots, and Shapiro-Wilk tests) and transformation will be done as necessary. Restricted maximum likelihood methods will be used to estimate the fixed effects and variance components. Additional outcomes (e.g., PCL-5, CAPS-5 symptom subscales) will be examined.

Hypothesis 3A: Prefrontal cortex-amygdala connectivity at rest and in response to alcohol/drug vs. neutral cues will predict reduction in alcohol/substance use severity (total standard drinks).

Hypothesis 3B: Prefrontal cortex-amygdala connectivity at rest and in response to trauma vs. neutral cues will predict reduction in PTSD severity (CAPS-5).

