
## Protocol: Glial Regulators for Testing Comorbid Posttraumatic Stress Disorder and Substance Use Disorders

regressed against the parameter estimate obtained from the center voxel from each cluster that exhibited a significant task x seed interaction with the AMY at rest and in response to the alcohol/drug cues (Hypothesis 3A). Changes in CAPS-5 total scores will be regressed against the parameter estimate obtained from the center voxel from each cluster that exhibited a significant task x seed interaction with the AMY at rest and in response to the trauma cue (Hypothesis 3B). Further exploratory analyses will examine change in PFC-AMY connectivity from pre- to post-treatment and associations with other alcohol/drug and PTSD outcomes, both within and between medication groups.

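### Hypothesis 3A fits an unadjusted linear regression to the change in total standard drinks, although Hypothesis 1 models that count with a log link and baseline adjustment; if drinking varies widely, much of the n=40 power can be lost

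*Combined protocol and SAP*

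**What the plan says.** All passages are in the Statistical Analyses part of the combined protocol and SAP.

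- **Hypothesis 3A and 3B, analysis.** "Separate linear regression tests will be used to test for associations between PFC-AMY connectivity at baseline and improvement in AUD/SUD"; the sentence goes on to cover PTSD symptoms as well. For 3A the outcome and predictor are given as "Changes in total standard drinks will be" "regressed against the parameter estimate obtained from the center voxel from each cluster that exhibited a significant task x seed interaction". No link function, transformation, baseline covariate, arm term, robust method or residual check is named.
- **Hypothesis 1.** Total standard drinks is a primary outcome. "A Poisson distribution will be assumed with a logarithm link function to assess the effects of NAC treatment". The plan adds: "Data collected in substance abuse studies often contain a preponderance of zeros". It continues: "If this excess is present in the distribution, two-part Hurdle models (Poisson and NB) will be explored". On adjustment: "Baseline alcohol/substance use and craving will be included in pertinent models as covariates".
- **Hypothesis 2.** Residual checks, with transformation if needed, are written here for CAPS-5 and nowhere else.
- **Neuroimaging Component.** The imaging subset is 40 people. Exclusions for head motion come off that number.

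**The concern.** One variable is handled in two incompatible ways. A log link says that an influence on drinking acts proportionally. Under a proportional effect, the absolute change scales with how much a person drank before. A fall from 600 to 300 drinks and a fall from 60 to 30 are both 50% reductions, but they enter the Hypothesis 3A regression as 300 and 30, a factor of ten. With 40 participants or fewer, the fitted slope can then reflect mainly the heaviest drinkers.

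Eligibility makes wide variation plausible, because any current alcohol or other substance use disorder qualifies.

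The missing baseline term raises a second issue. Change is baseline minus follow-up, so it contains baseline drinking. If connectivity is related to how much people drank on entry, it will appear to predict change even when it predicts nothing about response.

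Hypothesis 3A is a stated hypothesis of the trial. A real association could be missed, or a spurious one reported.

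**Working it through.** **1. The plan's own figure.** The power statement nearest to Hypothesis 3A (Power and Sample Size Estimation) gives N=34 for d=1.0, two-tailed alpha .05, power .80. For a two-sample t-test with 17 per group, the noncentrality is 1.0 × √(17/2) = 2.92 on 32 degrees of freedom, and power is 0.807. The figure reproduces.

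It concerns a two-group difference, not a slope. To convert: r = d/√(d²+4) = 1/√5 = 0.447. Power of a well-behaved linear regression is Φ(atanh(r)·√(n−3) − 1.96):
- n=34: Φ(0.481 × 5.57 − 1.96) = 0.76
- n=40: Φ(0.481 × 6.08 − 1.96) = 0.83

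The documents state no power, slope or correlation for the Hypothesis 3A regression itself.

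**2. Effect of the outcome scale alone.** Assumptions: n=40, true r=0.447 on the log-ratio scale, lognormal baseline drinks, no abstainers, 20,000 simulated trials per scenario.

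| Log-SD of baseline drinks | Power, log scale | Power, absolute change |
|---|---|---|
| 0.3 | 0.82-0.84 | 0.64-0.66 |
| 0.6 | 0.82-0.84 | 0.39-0.55 |
| 0.9 | 0.82-0.84 | 0.23-0.42 |
| 1.2 | 0.82-0.84 | 0.15-0.31 |

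Over 24 scenarios, including 25% abstinent at follow-up and a further 20% non-drinkers:
- The ratio of absolute-change power to the better log-scale power ran from 0.18 to 1.03.
- More than half the power was lost in 10 of the 24.
- The three most extreme participants supplied a median 38% to 79% of the outcome sum of squares.

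If the effect is additive in drinks, the linear model has power 0.85-0.88 and nothing is lost.

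**3. Planned model against a specific alternative.** Assumptions: n=40, baseline log-SD 0.5-1.2, residual log-SD 0.75, 30% fewer drinks per SD of connectivity, 0-25% abstainers at random.

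| Analysis | Power |
|---|---|
| Linear, change on connectivity (as planned) | 0.10-0.39 |
| Linear, change, plus raw baseline and arm | 0.25-0.57 |
| Negative binomial, log link, log baseline and arm, permutation p-value | 0.37-0.70 |

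Part of the gain comes from the covariates and part from the scale. Type I error of the permutation test was 0.05-0.075.

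**4. Type I error of the planned model.** With connectivity independent of drinking it stays near 0.05 (0.046-0.055 over all runs). With an assumed correlation of 0.3 between connectivity and baseline drinking, and no effect on response, it rises to about 0.22-0.30.

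**5. Sensitivity to the average fall in drinking.** The settings of step 3 were simulated again with a baseline median of 200 drinks and treatment-period drinks proportional to baseline^0.85. The median in those who drank was set at 30% or 50% of 200. There were 1,000 runs per setting, with log-SD 0.5 and 1.2 and abstainers 0 and 25%.

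| Quantity | Median 30% of baseline | Median 50% of baseline |
|---|---|---|
| Power as planned | 0.08-0.37 | 0.13-0.51 |
| Power, linear with baseline and arm | 0.25-0.60 | 0.25-0.57 |
| Power, negative binomial with permutation | 0.41-0.70 | 0.41-0.68 |
| Type I error as planned, correlation 0.3 | 0.24-0.30 | 0.11-0.22 |
| Type I error, linear with baseline and arm, correlation 0.3 | 0.05-0.06 | 0.04-0.06 |

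The ordering holds throughout. The inflation is smaller when drinking falls less, because baseline then makes up less of the change score.

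**6. Alternatives that do not work at this size.**
- Linear regression of log(drinks+1) fell to power 0.09-0.12 with 25% random abstainers, below the adjusted linear model.
- Negative-binomial regression with sandwich standard errors had Type I error of about 0.065-0.125.
- With model-based standard errors (dispersion fixed at 1) it was 0.07-0.09.

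**The case against.** The strongest defence is that an absolute reduction in drinks is a legitimate target. Hypothesis 3A asks about reduction in total standard drinks, and percent reduction is a different question. This stands as far as it goes: the linear model is not wrong in itself, and under an additive effect it loses nothing. It does not explain why the plan assumes proportional effects for the same variable under Hypothesis 1, nor why baseline is left out.

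A second defence is the general rule at the start of Statistical Analyses, that baseline characteristics associated with the primary outcomes become covariates. This could bring baseline drinks into Hypothesis 3A. But the rule depends on the data and names neither Hypothesis 3A nor arm. Step 3 shows that a raw baseline term recovers only part of the power.

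A reader might go further and infer that most of the power is lost and that a few very heavy drinkers decide the slope. The documents do not support this. They give no mean, SD, skewness or zero fraction for drinks, and the loss exceeded half in 10 of 24 assumed scenarios.

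A reader might also infer that the plan itself declares drinks to be zero-heavy and skewed. It says only that such data often contain many zeros, makes hurdle models conditional on seeing the excess, and never calls the variable skewed. Nor do follow-up zeros make a change score zero-heavy: baseline minus zero is baseline.

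Finally, this is a mechanistic hypothesis in a subset. The treatment comparisons in Hypotheses 1 and 2 are untouched.

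**Conclusion.** The mismatch is real and visible in the text: count model, log link and baseline adjustment under Hypothesis 1; linear regression of change, with no adjustment or diagnostics named, under Hypothesis 3A.

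The loss of power is conditional. It is large if baseline drinking varies widely and effects are proportional (about 0.10-0.39 as planned against 0.37-0.70 for the alternative). It is small if baseline drinking is homogeneous, and absent if the effect is additive.

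It would be too reassuring to say that the planned test always keeps its Type I error. That requires connectivity to be unrelated to baseline drinking. At an assumed correlation of 0.3 the error is about 0.22-0.30, or 0.11-0.22 if median drinking falls only by half. This part does not depend on a proportional effect of connectivity, and baseline adjustment removes it.

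All these sizes rest on assumed drink distributions. What does not rest on them is that the plan should state one scale and one baseline rule for this outcome before the data are seen.

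**What to change.** In the Hypothesis 3A analysis, replace the regression of change in drinks with the following:

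- **Outcome and model.** Treatment-period total standard drinks, in a negative-binomial regression with a log link.
- **Terms.** Connectivity as predictor; log(baseline drinks + 1) and treatment arm as covariates.
- **Test.** A permutation p-value, not one from model-based or sandwich standard errors.
- **Sensitivity analysis.** The linear model of absolute change, adjusted for baseline drinks and arm, with influence checks on the most extreme participants.
- **Avoid.** Linear regression of log(drinks+1) if abstinence is common.

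The TLFB baseline window is 60 days and treatment lasts 8 × 7 = 56 days, with no rescaling rule for the change. With log baseline as a covariate, that fixed difference in length no longer enters the outcome.

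This changes analysis wording only and needs no new data. The cost is that the effect is reported as a rate ratio per SD of connectivity and not as a difference in drinks; the sensitivity analysis still supplies the latter.
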